2.7.3 Handling of missing values/censoring/discontinuations

As a general rule, missing data will not be imputed in any secondary endpoint analyses. All the available data up to the end of treatment epoch date, irrespective of on or off study treatment will be used as applicable. Details of handling discontinuations or censoring are provided in the relevant endpoints or analysis of endpoints sections ([Section 2.7.1](#) and/or [Section 2.7.2](#)).

2.8 Safety analyses

Safety analyses will be conducted using the safety (SAF) set. Patients will be grouped by the actual treatment received. If patients received both investigational drug and active comparator

accidentally during the study, they will be analyzed according to the treatment to which they were exposed longer in duration. Unless explicitly stated otherwise, only data up to and including the safety cut-off of 100 days after last administration of study drug will be included in the analysis and data beyond this time point for a given patient will be excluded from the safety analysis. The safety cut-off of 100 days (5 x 20 days) takes the long half-life of both the investigational and comparator-drug into account.

The assessment of safety will be primarily based on the frequency of adverse events (including death and non-fatal serious adverse events). Additional safety assessments include laboratory tests, physical examination (including examination of skin), vital sign measures, ECG evaluations and assessment of suicidality. Clinically significant findings in these additional safety assessments will be reported as adverse events and analyzed as such. In addition all safety assessments will be summarized or listed as appropriate.

2.8.1 Adverse events (AEs)

An adverse event (AE) is any untoward medical occurrence (i.e., any unfavorable and unintended sign [including abnormal laboratory findings], symptom or disease) in a patient or clinical investigation of a patient after providing written informed consent for participation in the study. That means that a patient can report AEs before having started study medication. For reporting purposes, the main focus will be on treatment emergent adverse event (TEAE), defined as any adverse event which started on or after the day of first dose of study medication.

Except for serious TEAEs and death, only TEAEs up to and including safety cut-off of 100 days after last administration of study drug will be included in the analyses. All serious TEAEs and death will be included, regardless of safety cut-off.

AEs will be reported by primary system organ class (SOC) and preferred term according to the Medical Dictionary for Regulatory Activities (MedDRA). The MedDRA version used for reporting the study will be described in a footnote.

The number and percentage of patients reporting any TEAEs (referred to as incidence of any TEAEs later) will be summarized by primary SOC, preferred term and treatment. Separate summaries will be provided for serious TEAEs, drug related TEAEs, TEAEs leading to permanent discontinuation of study drug, TEAEs causing study drug interruption, and most common TEAEs ($\geq 2\%$ in any of the treatment groups). Additionally, incidence of any TEAEs will also be summarized by SOC, preferred term, and maximum CTCAE grade. Missing CTCAE grade will not be imputed..

Odds ratios (investigational drug vs. control) with 95% confidence intervals will be presented along with the summary of any TEAEs and the summary of serious TEAEs. Details in calculations of odds ratios and their 95% confidence intervals are provided in [Section 5.7.1](#). Incidence of any TEAEs will be plotted by SOC, along with the odds ratio (and corresponding 95% confidence interval) for TEAEs in each SOC. Odds ratios provide appropriate inferences for events that are likely to occur at certain times (e.g., injection related reactions) while no constant risk over time is expected.

Given the flexible duration of patients follow-up in the study, any TEAEs and serious TEAEs will also be summarized by reporting exposure-adjusted incidence rates (assuming a Poisson-process for adverse events), by primary SOC, preferred term and treatment. The analysis will

take into account the time-at-risk as defined in [Section 2.4.1](#) for each patient. The incidence rate ratios (investigational drug vs. control) and corresponding 95% confidence intervals will be presented along with this summary. Details in calculations of incidence rates and their 95% confidence intervals as well as incidence rate ratios and their 95% confidence intervals are provided in [Section 5.7.2](#). The exposure adjusted incidence rates provide appropriate inferences for events that are likely to occur at any time during the observation period with constant risk over time (e.g., infection or cancer).

If a patient reported more than one adverse event within the same primary system organ class, the patient will be counted only once with the maximum CTCAE grade at the system organ class level, where applicable.

All AEs will be presented in listings.

For the subgroup of patients who accidentally received both investigational drug and active comparator during the study, a listing of adverse events along with drug administration information will be provided.

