7.2 Serious adverse events

7.2.1 Definition of SAE

An SAE is defined as any adverse event [appearance of (or worsening of any pre-existing)] undesirable sign(s), symptom(s) or medical conditions(s) which meets any one of the following criteria:

- is fatal or life-threatening
- results in persistent or significant disability/incapacity
- constitutes a congenital anomaly/birth defect
- requires inpatient hospitalization or prolongation of existing hospitalization, unless hospitalization is for:
 - routine treatment or monitoring of the studied indication, not associated with any deterioration in condition (e.g. hospitalization for MS relapse treatment)
 - elective or pre-planned treatment for a pre-existing condition that is unrelated to the indication under study and has not worsened since signing the informed consent
 - treatment on an emergency outpatient basis for an event not fulfilling any of the definitions of a SAE given above and not resulting in hospital admission
 - social reasons and respite care in the absence of any deterioration in the patient's general condition
- is medically significant, e.g. defined as an event that jeopardizes the patient or may require medical or surgical intervention.

All malignant neoplasms will be assessed as serious under “medically significant” if other seriousness criteria are not met.

Life-threatening in the context of a SAE refers to a reaction in which the patient was at risk of death at the time of the reaction; it does not refer to a reaction that hypothetically might have caused death if it were more severe.

Medical and scientific judgment should be exercised in deciding whether other situations should be considered serious reactions, such as important medical events that might not be immediately life threatening or result in death or hospitalization but might jeopardize the patient or might require intervention to prevent one of the other outcomes listed above. Examples of such events are intensive treatment in an emergency room or at home for allergic bronchospasm, blood dyscrasias or convulsions that do not result in hospitalization or development of dependency or abuse.

Any suspected transmission via a medicinal product of an infectious agent is also considered a serious adverse reaction.

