- **Time at risk for AE** is defined as the number of days spent in the study, from first to last administration of study drug, plus the safety data cut-off of 100 days. Time at risk for AE will be used for tables reporting AEs (including both SAE and non-SAE). If the corresponding last day of time at risk for AE is after the analysis cut-off date, then it will be truncated by the analysis cut-off date as defined in [Section 2.1](#).
- **Time at risk for SAE** is defined as the number of days spent in the study from the day of first administration of study drug to the end of study date (including safety follow up epoch). Time at risk for SAE will be used only for tables reporting SAEs. If a patient is still in safety follow up epoch at the time of reporting, time at risk for SAE is the number of days from the day of first administration of study drug to the analysis cut-off date as defined in [Section 2.1](#).

Time at risk for AE and time at risk for SAE will be summarized in a similar way to duration of exposure to study drug.

Compliance to the study drug administration schedule will be calculated as duration of exposure to study drug in (days)/duration of on-treatment period (as defined in [Section 2.1.1](#)) in (days) $\times 100\%$. This rule means that compliance will be measured during the time interval the patient took study medication: premature discontinuation from study drug will not be considered non-compliance. Compliance to study drug administration will be summarized descriptively on SAF by treatment group. In addition, compliance will be summarized with cumulative number and percentage of patients in each compliance category (*i.e.*, $\geq 20\%$, $\geq 30\%$, $\geq 40\%$, $\geq 50\%$, $\geq 60\%$, $\geq 70\%$, $\geq 80\%$, $\geq 90\%$, $\geq 95\%$, $\geq 98\%$, $=100\%$).

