5.7.2 Exposure adjusted incidence rate and 95% confidence interval

It will be assumed that for each of n patients in a clinical trial the time t_j ($j=1, \dots, n$) to the first incidence of a certain event is observed, or if the event was not experienced, the time is censored at the end of the observation period. The sequence of first occurrences of an event will be modeled to follow approximately a Poisson process θ with constant intensity λ . The rate parameter λ will be estimated by $\hat{\lambda} = \frac{D}{T}$, where $T = \sum_{j=1}^n t_j$ and D is the number of patients with at least one event. Conditionally on T, an exact 95% confidence interval for a Poisson variable with parameter θT and observed value D can be obtained based on ([Garwood, 1936](#)), from which an exact 95% confidence interval for $\hat{\lambda} = \frac{D}{T}$ will be derived as follows ([Sahai, 1993](#); [Ulm, 1990](#)):

Lower confidence limit $L = \frac{0.5c_{\alpha/2, 2D}}{T}$ for $D > 0$, 0 otherwise,

Upper confidence limit $U = \frac{0.5c_{1-\alpha/2, 2D+2}}{T}$

where $c_{\alpha, k}$ is the α^{th} quantile of the Chi-square distribution with k degrees of freedom.

The SAS procedure GENMOD will be used to fit a Poisson regression model with only treatment as factor, the log-link and natural logarithm of time as the offset variable. The incidence rate (and 95% confidence intervals) are obtained as the exponentiated estimates by treatment (e.g. obtained by statement LSMEANS with option EXP). The data set will include a patient level response variable indicating whether the patient experienced at least one event of a specific type (1=yes, 0=no) and a patient level time variable which is derived as follows:

- For patients who had at least one event of that type: time is calculated as (start day of the first event - date of first administration of study drug+1).
- For patients who did not have an event of that type: time at risk as defined in [Section 2.4.1](#) will be used.

The time will be divided by 365.25 before taking the logarithm transformation as offset variable so that the estimated incidence rate corresponds to an annualized rate.

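### Exposure-adjusted tables that mix serious and non-serious events count serious events without a time limit but stop event-free patients' time at risk at last dose + 100 days

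*SAP*

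**What the plan says.** **Events counted (SAP 2.8.1).** A TEAE is "defined as any adverse event which started on or after the day of first dose of study medication", with no end date. The reporting limit is "Except for serious TEAEs and death, only TEAEs up to and including safety cut-off of 100 days after last administration of study drug". Serious events are exempt: "All serious TEAEs and death will be included, regardless of safety cut-off". Protocol 9.5.2.1 has the same exemption. Neither document confines the exemption to SAE-only tables.

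**Time at risk (SAP 2.4.1).** There are two versions.
- The AE version runs "from first to last administration of study drug, plus the safety data cut-off of 100 days", truncated at the analysis cut-off if that is earlier. On its use: "Time at risk for AE will be used for tables reporting AEs (including both SAE and non-SAE").
- The SAE version runs "from the day of first administration of study drug to the end of study date (including safety follow up epoch") and serves only tables that report SAEs.

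**Estimator (SAP 5.7.2).** The rate is D/T, where D is the number of patients with at least one event. A patient with the event contributes time from first dose to that event, however late it falls. For the others: "For patients who did not have an event of that type: time at risk as defined in" SAP 2.4.1.

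**Tables affected.** SAP 2.8.1 and 2.8.1.1 apply this estimator to any TEAE and to all TEAEs matching the AESI search terms. Serious AESI have separate summaries.

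**The concern.** A first serious event 200 days after the last dose counts in the any-TEAE and AESI rate tables. A patient observed to the same day without an event is credited only to day 100. Person-time beyond the window is thus admitted only when it ends in an event, and D/T no longer estimates a constant rate. SAP 2.4.1 itself says that time at risk matches the period used for reporting adverse events, and protocol 9.3 says much the same. For serious events in mixed tables it does not.

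Late serious events will be captured. Protocol 3.1 requires at least 9 months of follow-up after drug discontinuation for patients who do not enter the extension, and protocol 7.2.2 collects SAEs up to the EOS or End of Safety FU visit.

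SAP 2.8.1 names infection and cancer as the events for which exposure-adjusted rates suit best. Protocol 7.2.1 states: "All malignant neoplasms will be assessed as serious under" the medically significant criterion. Malignancy, a main use of the table, is therefore the event type most exposed to the mismatch.

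**Working it through.** The documents state no adverse event rate, so there is no plan figure to reproduce. The check covers mechanism and size.

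**Inputs.** From the documents: window c = 100/365.25 = 0.274 y; off-drug follow-up of at least 9 months = 0.75 y; planning follow-up T = 1.5 y (SAP 3.1.1.1). Assumed, because the documents do not give them: the share d who stop drug and stay under observation (10–30%), stopping times uniform over T, a constant hazard on and off drug, and the event rates.

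**Mechanism.** Take 100 patients, each 1.5 y on drug and 0.75 y followed off drug. Three have a serious event before the cut-off (mean 0.9 y) and one has it at 2.0 y.
- As written: 4 / (3×0.9 + 2.0 + 96×1.774) = 4/175.0 = 2.29 per 100 patient-years.
- Both windows at +100 days: 3 / (2.7 + 97×1.774) = 3/174.8 = 1.72.
- Both windows at end of follow-up: 4 / (2.7 + 2.0 + 96×2.25) = 4/220.7 = 1.81.

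The as-written rate exceeds both matched rates.

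**Size for a rare, always-serious event.** The relative excess is about F/W, where F is observed time beyond the window and W is credited time.

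A patient who stops at time s is credited s + c, on average 0.75 + 0.274 = 1.024 y. If observed to the later of EOS and s + 0.75, the mean time observed off drug is 0.5×0.75 + 0.5×1.125 = 0.9375 y, so F per stopper is 0.9375 − 0.274 = 0.664 y.

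- A. Completers credited to EOS only: 0.664d / [1.024d + 1.5(1−d)].
- B. Completers also credited +100 days, as SAP 2.4.1 provides: 0.664d / [1.024d + 1.774(1−d)].
- C. All data truncated at EOS (roughly the registration CSR): F per stopper = (1.5−0.274)²/(2×1.5) = 0.501 y, giving 0.501d / (1.5 − 0.501d).
- D. A share d has 1.5 y on drug and then exactly 9 months off drug; the rest end at 1.5 y: 0.476d / (1.5 + 0.274d), where 0.476 = 0.75 − 0.274.

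| | d = 10% | d = 20% | d = 30% |
|---|---|---|---|
| A | 4.6% | 9.4% | 14.7% |
| B | 3.9% | 8.2% | 12.9% |
| C | 3.5% | 7.2% | 11.1% |
| D | 3.1% | 6.1% | 9.0% |

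Applying the SAP 5.7.2 estimator to 2,000,000 simulated patients under D, with a serious rate of 0.02/y, gave ratios of as-written to matched rate of 1.03 (d = 10%) and 1.06 (d = 20%). With both windows at +100 days it returned the true 0.020/y.

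**Size for a mixed AESI.** The excess shrinks by the serious fraction: about F/W × λs/(λs+λn), with λs and λn the serious and non-serious rates. Under D with d = 20%, F/W = 0.061.
- λs = 0.02, λn = 0.02: 0.061×0.5 = 3.1% (simulated 1.03).
- λs = 0.01, λn = 0.1: 0.061×0.091 = 0.6% (simulated 1.005).

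**Rate ratio.** With equal d and equal late hazard relative to the earlier hazard in both arms, the same factor applies to both rates and cancels.

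**The case against.** **Intent.** The exemption for serious events may have been meant only for SAE and death reporting, and the SAP 2.4.1 statement that risk time matches the reporting period supports that. This is a fair reading of intent, but neither document says so. A programmer who follows SAP 2.8.1, 2.4.1 and 5.7.2 literally produces the mismatch.

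**The matched rate is available elsewhere.** SAE-only and serious-AESI tables use the SAE time at risk. For malignancy, a matched rate would therefore appear alongside the distorted one. This stands and limits the harm.

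**Size.** A reader might take the plan's 20% dropout allowance as the share who stop drug and are followed, and so put the inflation at about 9%. The documents do not support that: SAP 3.1.1.1 assumes those patients contribute nothing to the primary analysis. Row A also withholds from completers the 100 days that SAP 2.4.1 gives them. The 27% and 30% discontinuation figures cited there from earlier teriflunomide trials do not say how many patients stayed under observation either.

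**Treatment comparison.** A reader might infer a biased rate ratio. A 10% versus 30% split of stoppers would shift it by 1.147/1.046 = 1.097 under row A, but no such split appears anywhere, and SAP 3.1.1 plans for dropouts equally distributed across arms.

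**Direction.** A reader might conclude that all AESI rates are inflated. Mixed AESI barely move. In the final CSR an opposite error could also offset the inflation. If every completer entered the extension and were credited 100 days not observed in this study, then with d = 20% observed time would be 0.2×(0.75+0.9375) + 0.8×1.5 = 1.54 y, against 0.2×1.024 + 0.8×1.774 = 1.62 y credited. The as-written rate would then be about 5% low. That is a separate matter of truncation, but it rules out a flat claim that published rates will be too high.

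**Conclusion.** The mismatch is real on the text and runs against the SAP's own principle that risk time and reporting period coincide. Late serious events push mixed-table rates upward. The overstatement is roughly 3–15% for an always-serious event with constant hazard if 10–30% of patients stop drug and all are followed, and about 0.5–3% for AESI that mix serious and non-serious events at the assumed rates.

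These are conditional figures. There is no inflation without late serious events, less if not all stoppers are followed, and less if the hazard falls off drug. The documents fix none of these quantities. They do not support a claim of material inflation across AESI, or of bias in the rate ratio without a difference between arms in off-drug follow-up or late serious events. The point is worth correcting because it falls on rare, serious risks and the remedy is short.

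**What to change.** In SAP 2.8.1 and 5.7.2, state that every exposure-adjusted table using the AE time at risk counts all events, serious or not, only up to last dose + 100 days, or the analysis cut-off if earlier. A patient whose first event falls later is treated as event-free in that table. Keep later serious events in the SAE and serious-AESI tables with the SAE time at risk.

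Lengthening the denominator of the mixed tables is not an equivalent remedy. Non-serious events after day 100 are not counted, so their rates would then be understated.

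The cost is small but not nil:
- The rule departs from protocol 9.5.2.1 for these rate tables and should be listed in SAP Section 4.
- Event counts in the rate tables may differ from those in the matching incidence and odds-ratio tables, which needs a footnote.

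No late serious event is lost from the report. The change does not settle how the 100 days are credited to patients who enter the extension; that needs its own rule.

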2.8.1.1 Selected AEs of special interest / grouping of AEs

Selected tables will be produced for Adverse Events of Special Interest (AESI) (i.e., risks) defined in the latest version of case retrieval sheet (eCRS) at the time of analysis implementation (i.e., study database lock). Specifically, incidence of TEAEs that fulfill the risk search terms as defined in eCRS will be summarized by risk name, preferred term and treatment with odds ratios and 95% confidence intervals presented. The exposure-adjusted incidence rate of TEAEs that fulfill the risk search terms as defined in eCRS will also be summarized by risk name, preferred term and treatment with incidence rate ratios and 95% confidence intervals presented. Similarly, separate summaries will be provided for serious TEAEs that fulfill the risk search terms as defined in eCRS. Additionally, incidence of any TEAEs that fulfill the search terms as defined in eCRS will also be summarized by risk name, preferred term, and maximum CTCAE grade.

2.8.1.1.1 Injection reaction related AEs

Incidence of injection site reaction AEs and injection systemic reaction AEs as collected in the relevant CRF pages will be reported as part of the AE summary tables as two preferred terms respectively. For summaries of injection systemic reaction AEs specified in this section, , reaction/symptom start date and time will be compared with the injection date and time. Only reactions/symptoms within 24 hours after injections will be included (i.e., time to onset of reaction \leq 24 hours). The time to onset of reaction will be derived as (reaction start date/time – injection date/time) and rounded to the closest integer in hours.

Symptoms listed in the injection site reaction or injection systemic reaction CRF pages will be summarized by providing the number and percentage of patients with each of the symptoms and pre-specified grouping of symptoms as well as overall. These summaries will be provided for each injection up to injection 10 and cumulatively for all injections.

For the injection site reaction, no grouping of symptoms will be specified. For the injection systemic reaction, symptoms will be grouped under 6 categories as defined below and the

number and percentage of patients with at least one symptom reported under the category will be provided for each category.

- Skin/mucosal tissue symptoms: Rash, Urticaria, Pruritus general, Flushing
- Respiratory compromise: Dyspnea, Bronchospasm, Chest discomfort, Cough
- Related to change in vital signs: Hypotension, Hypertension, Dizziness, Tachycardia
- Gastrointestinal symptoms: Nausea, Vomiting, Abdominal pain, Diarrhea
- Musculoskeletal/connective tissue symptoms: Arthralgia, Myalgia, Back pain
- Other manifestations: Fever, Headache, Chills, Asthenia, Fatigue, and Other

For the injection systemic reaction, time to onset of the first symptoms after each injection will be summarized by cumulative hour intervals (i.e., 0 to 1, 0 to 2, 0 to 3, etc. until 0 to 24 hours). These summaries will be provided for each injection up to injection 10 and cumulatively for all injections.

The proportion of patients with injection site reactions and the proportion of patients with injection systemic reactions will be plotted by treatment group against the injection sequence numbers (injections 1, 2, 3, 4, 5, 6, 7, 8, 9 and 10).

For the first 3 injections, additional summaries will be provided by category of injection related premedication. Specifically, 9 categories are defined as 1) no injection related premedication, 2) type 1, 3) type 2, 4) type 3, 5) type 1+ type 2, 6) type 1+ type 3, 7) type 2+ type 3, 8) type 1+ type 2+ type 3, 9) Any injection related premedication. The types 1 to 3 refer to protocol specified three types of injection related premedication as stated in [Section 2.4.2.3](#).

A separate listing for injection site reaction AEs and injection systemic reaction AEs will be provided where all reported injection related reactions (IRR) (regardless of timing) will be listed along with the corresponding injection sequence number and time to onset from the most recent injection as well as from Day 1. The listing will be sorted by injection of first occurrence of symptoms. Specifically, under the first injection, patients whose first IRR was associated with the first injection will be listed; within a patient all IRRs to all injections will be listed chronologically. Under the second injection, patients whose first IRR was associated with the second injection will be listed; similarly, within a patient all IRRs to all injections will be listed chronologically. The listing will continue with subsequent injections until all patients with IRRs are included in the listing.

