In study OMS112831 of sc ofatumumab, the most commonly reported AEs across the ofatumumab dose groups were injection-related reactions (52% for ofatumumab, 15% for placebo). Injection-related reactions occurred primarily post-first dose, diminished on subsequent dosing and were mostly mild/moderate in severity (97% of the events). There were no notable differences across treatment groups in the overall incidence of infection-related AEs, including urinary and respiratory tract infections. Few serious adverse events (SAEs) were reported. These were mainly systemic injection-related reactions (3 patients), all occurring on

Day 1 and in the 60 mg ofatumumab dose groups. There were no cases of opportunistic infections reported during the study.

For further details about ofatumumab, please refer to the Investigator's Brochure.

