In order to assess tolerability of the initial dose of study medication (injectable + oral), patients will be closely monitored following administration for any reactions including injection related. Patients must remain at the site under observation for a minimum of approximately **5 hours** following dosing on Day 1.

On Day 7 and Day 14, the same time-window (+/- 1 day) as for study visit applies. Starting at week 4, the subcutaneous injections should be administered at 4-week (28 days) intervals (+/- 3 days). Injections may not be advanced by more than 3 days. The patient should be instructed to record any missed doses in the patient diary provided for the study and to inform the study staff of any missed sc injection(s). This can be done at the visits and/or during the monthly structured telephone interviews (according to the script provided to the sites for the study) during which the study site staff will inquire about the patient's status and compliance with study drug administration or issues related to the home administration.

Patients, who miss sc injections or temporarily interrupt study drug without discontinuing from the study or withdrawing consent, will be permitted to resume study drug if determine to be safe and appropriate in the opinion of the Investigator. When resuming study drug, the timing of the next sc injection will be determined based on the original study schedule as followed:

- If one monthly injection is missed by 1 week or less, the patient should take the injection as soon as possible. The next injection should then be administered according to the original schedule.

- If one monthly injection is missed by more than 1 week, the patient should skip the dose and take the next dose at the time when the next injection would be due according to the original schedule.
- If 2 or more consecutive monthly injections are missed, the Investigator should inform the local Sponsor Medical Advisor before re-starting dosing. Missed injection syringes should not be used and returned to the site at the next visit.

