If a patient misses any daily capsules, daily dosing should be resumed as soon as possible (i.e. patients should not compensate for a missed dose by increasing the frequency on subsequent doses). The patient should be instructed to record any missed doses in the patient diary provided for the study and to inform the study staff at the next visit or during the monthly telephone interview of any missed doses. The patient should be instructed to return any missed doses. If more than 3 consecutive months are missed, resumption of oral dosing should only be initiated if it is determined to be safe and appropriate in opinion of the Investigator.

All kits of study medication assigned by the IRT will be databased in the IRT system.

All dosages prescribed to the patient and all dose interruptions/changes during the study must be recorded on the Dosage Administration Record eCRF.

The Investigator must promote compliance by instructing the patient to take the study medication exactly as prescribed and by stating that compliance is necessary for the patient's safety and the validity of the study. The patient must also be instructed to contact the Investigator if he/she is unable for any reason to take the study treatment as prescribed.

The patients will record information concerning their home study drug administrations in a diary provided for the study. The information to be recorded includes date and time of each sc injection and any symptoms related to the administration as well as any missed doses of study drug. The Investigator will review the diary with the patient at each visit and record the information on the relevant eCRFs.

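### Onset times of systemic injection reactions are rounded to the nearest hour before being tabulated, so each cumulative row also counts onsets up to about 29 minutes past its limit

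*SAP*

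**What the plan says.** SAP 2.8.1.1.1 (Injection reaction related AEs) compares the start date and time of each reaction or symptom with the date and time of the injection. It limits the systemic-reaction summaries to early onsets: "Only reactions/symptoms within 24 hours after injections will be included". Time to onset is the difference between the two date/times, "rounded to the closest integer in hours". This derivation is introduced with the words "For summaries of injection systemic reaction AEs specified in this section", so it governs the tables and not only a listing.

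For systemic reactions, "time to onset of the first symptoms after each injection will be summarized by cumulative hour intervals", running from 0 to 1 hour up to 0 to 24 hours, for each injection up to the tenth and for all injections together. No second, unrounded onset variable is defined, and the section does not say in which order the 24-hour limit and the rounding are applied.

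On the data behind it, Protocol 5.5.4 says of the patient diary for home administration: "The information to be recorded includes date and time of each sc injection and any symptoms related to the administration".

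**The concern.** A cumulative row labelled 0 to 1 hour should hold reactions that began within 60 minutes. If the variable compared with the limit has already been rounded to the nearest hour, an onset at 1 h 25 min becomes 1 and is counted there, and an onset at 5 h 20 min is counted in 0 to 5.

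The error in the cumulative counts cannot cancel. Rounding up (40 minutes to 1 hour) leaves a reaction in the row where it belongs. Rounding down brings a reaction into a row whose limit it has already passed.

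At stake is the accuracy of the table showing how soon systemic reactions start after each injection. The effect is largest in the first rows, where early onset is read off.

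**Working it through.** The plan states no figure for this table, so there is none to reproduce. The check has three steps.

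**1. Which onsets fall in each row.** Inputs: the rounding rule and the row limits in SAP 2.8.1.1.1. Assumptions: times recorded to the minute, halves rounded up. An onset of m minutes is counted in row 0 to k if floor(m/60 + 0.5) ≤ k, that is, if m < 60k + 30.

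- 0 to 1 h: last minute counted is 89 (29 minutes late)
- 0 to 2 h: last minute counted is 149 (29 minutes late)
- 0 to 3 h: last minute counted is 209 (29 minutes late)
- 0 to 24 h: last minute counted is 1469 (29 minutes late), if the 24-hour limit also uses the rounded value

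**2. Size under a simple onset model.** The documents do not give onset in hours. Protocol 1.1 describes only the pattern across doses: "Injection-related reactions occurred primarily post-first dose, diminished on subsequent dosing". ASSUMPTION: exponential onset, F(t) = 1 − 2^(−t/median), with a median of 2, 4, 6 or 8 hours. The true share of included reactions is F(k)/F(24). The reported share, if the rounded value also drives the 24-hour limit, is F(k+0.5)/F(24.5).

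Example, median 2 h, row 0 to 1: F(1) = 1 − 2^(−0.5) = 0.2929 and F(1.5) = 1 − 2^(−0.75) = 0.4054. F(24) and F(24.5) are both about 0.9998. The shares are 29.3% and 40.5%, a relative excess of 38%.

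| Median | 0–1 h true / reported | Excess | 0–2 h true / reported | Excess | 0–5 h true / reported | Excess |
|---|---|---|---|---|---|---|
| 2 h | 29.3 / 40.5% | 38% | 50.0 / 58.0% | 16% | 82.34 / 85.15% | 2.81 points |
| 4 h | 16.2 / 23.2% | 44% | 29.8 / 35.7% | 20% | 58.88 / 62.34% | 3.46 points |
| 6 h | 11.6 / 16.9% | 45% | 22.0 / 26.7% | 21% | 46.80 / 49.97% | 3.17 points |
| 8 h | 9.5 / 13.8% | 46% | 18.2 / 22.1% | 22% | 40.18 / 43.06% | 2.88 points |

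If the 24-hour limit uses the unrounded difference instead, the reported share becomes F(k+0.5)/F(24). The 0 to 1 h excess is then 38 to 47% and the 0 to 5 h excess 2.8 to 3.5 points, so the result does not depend on how that ambiguity is resolved.

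**3. Sensitivity to the assumed distribution.** Relative excess is F(k+0.5)/F(k) − 1. For the 0 to 1 h row:

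- uniform: 1.5/1 − 1 = 50%
- exponential with mean 0.5, 1, 2, 4 and 8 h: 9.9%, 22.9%, 34.1%, 41.4% and 45.5%
- log-normal, median 2 h, log-SD 1.0: 58.5%
- gamma, shape 2, mean 3 h: 83.1%
- log-normal, median 2 h, log-SD 0.5: 241% (true share 8.3%, reported 28.3%)

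If the onset density does not rise over the first 1.5 hours, the half hour after 60 minutes holds at most half of what the first hour holds, so 50% is then the ceiling. If onset peaks after the first hour, the excess can be larger. In all the distributions tried, the excess in the 0 to 6 h row lies between 0 and 8.3%, and in the 0 to 24 h row it is at most 2.1%.

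**The case against.** Several points on the other side stand.

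- The table is descriptive, without a test, and the rule is the same in both arms. Symptom frequencies and the incidence plot by injection number do not use the hour rows.
- A reader might infer that early onset is overstated by up to about half throughout. The documents do not support that. The figure fits one row, 0 to 1 h, under a flat onset density. With other densities that row may be much less or much more affected, and the effect fades quickly in later rows.
- A reader might infer that an onset at 24 h 20 min will certainly be included. The text does not settle this. It speaks first of comparing date and time, then of the 24-hour limit, and only then of rounding, which can be read as a limit on the unrounded difference. However, the limit is also written in terms of the onset variable that is then rounded. This is an ambiguity, not a shown error.
- A reader might infer that the table determines the Day 1 observation period or the advice on home injection. Nothing in the documents ties it to either. Protocol 5.5.4 already sets the observation rule ("Patients must remain at the site under observation for a minimum of approximately" 5 hours), and Protocol 5.5.7 bases home premedication on the experience with the first four injections.
- Rounding moves individual onset values both ways (1 h 40 min becomes 2 h). Only the cumulative counts shift in one direction.

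One further objection stands in part. Protocol 5.5.4 asks for date and time of injections but does not explicitly ask for the clock time of symptoms. If onset times are approximate, cut-offs to the minute may suggest more precision than the data have. That does not justify rounding before classification, because the SAP already computes the date/time difference and rounding adds an avoidable one-way error in the counts.

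**Conclusion.** The point holds as a minor defect. On the natural reading of SAP 2.8.1.1.1, each row 0 to k hours counts onsets up to about k hours 29 minutes, so the counts, and the shares on a fixed denominator, are overstated or unchanged. That conclusion needs no distributional assumption beyond times recorded to the minute; only the size does.

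Assuming exponential onset with a median of 2 to 8 hours, the 0 to 1 h row is about 38 to 46% too high in relative terms. It would be 50% if onset is uniform, less if onset is strongly front-loaded, and more if it peaks after the first hour. The 0 to 5 h row is about 2.8 to 3.5 percentage points too high, and later rows are little affected.

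Whether onsets between 24 h and 24 h 29 min are included is unclear from the text. Overall incidence is essentially unaffected either way, and no efficacy or confirmatory result is touched.

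**What to change.** State in SAP 2.8.1.1.1 that the cumulative hour rows are assigned, and the 24-hour limit applied, using the unrounded difference between reaction and injection date/time, and that rounding to whole hours is for display in listings only. This also settles the order of the two steps.

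The cost is a sentence in the SAP and a change to one derivation; no new data are needed. The SAP already carries an addendum made after database lock, so the change would need a further documented revision and a rerun of any onset table already produced. That addendum corrected another descriptive safety summary (B-cell depletion), so there is a precedent.
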